- o Respiratory rate ≥ 20 breaths per minute, $\text{SpO}_2 > 93\%$ on room air at sea level, or heart rate ≥ 90 beats per minute.

OR

Severe COVID-19

- Symptoms suggestive of severe systemic illness with COVID-19, which could include shortness of breath at rest or respiratory distress; and
- Respiratory rate ≥ 30 breaths per minute, heart rate ≥ 125 beats per minute, or $\text{SpO}_2 \leq 93\%$ on room air at sea level or $\text{PaO}_2:\text{FiO}_2 < 300$.

Note: Patients receiving high flow oxygen by a nasal cannula or noninvasive positive pressure ventilation are permitted.

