9.2.1 Analysis of Efficacy

Continuous efficacy endpoints will be analyzed using an analysis of variance model with effects for treatment and disease severity as factors.

Binary efficacy endpoints will be analyzed using a Cochran-Mantel-Haenszel test stratified by disease severity.

For all efficacy endpoints that do not include death as a possible outcome, data from subjects who die prior to Day 28 will be imputed at Day 28 based on the worst outcome.

All efficacy analyses will be performed using the ITT Population. The efficacy analyses will be repeated on the PP Population.

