- j. If a 12-lead electrocardiogram was performed within 24 hours prior to informed consent, it is not necessary to repeat the 12-lead electrocardiogram at Screening.
- k. Vital signs will include blood pressure, heart rate, SpO₂ (for non-ventilated subjects only), and respiratory rate. If vital signs are to be assessed at the same time point as a blood draw, vital signs should be assessed prior to blood draw. Vital signs will be assessed within 1 hour prior to each dose of study drug and 30 (\pm 15) minutes, 60 (\pm 15) minutes, and 90 (\pm 15) minutes following each dose of study drug. Additionally, after the first dose of study drug, supine blood pressure will be assessed every 5 (\pm 1) minutes for the first 15 minutes, and then every 15 (\pm 5) minutes for the first hour. Subjects will be in the supine position during dosing, and they must remain supine with their head no higher than 45° until the vital sign assessment is completed 90 minutes following dosing. After the Treatment Period, vital signs will be assessed daily until Day 28, unless discharged.
- l. ABG should be obtained only if clinically indicated. If ABG is obtained, the subject's current oxygen requirement should also be recorded.
- m. During the Treatment Period, SpO₂:FiO₂ or PaO₂:FiO₂ (if ABG is being performed per standard of care) will be assessed TID, within 1 hour prior to each dose of study drug. After the Treatment Period, SpO₂:FiO₂ or PaO₂:FiO₂ (if ABG is being performed per standard of care) will be assessed daily until Day 28, unless discharged.
- n. During the Treatment Period, clinical status will be assessed TID, within 1 hour prior to each dose of study drug, using the NIAID 8-point ordinal scale. After the Treatment Period, clinical status will be assessed once daily until Day 28, unless discharged. If the subject is discharged alive prior to Day 28, clinical status will be assessed at the Post-Treatment Observation Period telephone visits only.
- o. For all subjects remaining hospitalized on Day 14 or beyond, blood sampling for biomarkers will also occur on Day 28 or the day of hospital discharge, whichever occurs first.
- p. Vascular leakage and inflammation biomarker (Angpt-2, IL-6, IL-8, TNF α , and HMGB-1) analysis will be performed at a central laboratory.
- q. After it is determined that all eligibility criteria have been met, the subject will be randomized.

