3 STATISTICAL METHODOLOGY

3.1 General Considerations

3.1.1 *Analysis Day*

Analysis day will be calculated from the date of first dose of study drug. The day of the first dose of study drug will be Day 1, and the day immediately before Day 1 will be Day -1. There will be no Day 0.

3.1.2 *Definition of Baseline*

Baseline is defined as the last measurement prior to the first dose of study drug.

3.1.3 *Visit Windows*

No analysis visit windows will be defined for this study, i.e., the nominal visits /time-points will be used for all statistical summaries/analyses.

3.1.4 *Summary Statistics*

Categorical data will generally be summarized with counts and percentages of subjects. The denominator used for the percentage calculation will be clearly defined. Continuous data will generally be summarized with descriptive statistics including n (number of non-missing values), mean, median, standard deviation, minimum, and maximum.

Summaries of change from baseline variables will include only patients who have both a baseline value and corresponding value at the post-baseline time point of interest.

3.1.5 *Hypothesis Testing*

All statistical comparisons will be made using two-sided tests at $\alpha = 0.05$. All null hypotheses will be of no treatment difference, and all alternative hypotheses will be two-sided. Confidence intervals will be two-sided, unless stated otherwise.

3.1.6 *Handling of Dropouts and Missing Data*

For all efficacy endpoints that do not include death as a possible outcome, data from subjects who die prior to Day 28 will be imputed at Day 28 based on the worst outcome. Other missing data for selected endpoints will be imputed using the methods as described in Section 3.4.

In cases of missing or incomplete dates (e.g. AE and concomitant medications), the missing component(s) will be assumed as the most conservative value possible. For example, AEs with missing start dates, but with stop dates either overlapping into the treatment period or missing,

will be counted as treatment-emergent, taking the worst-case approach. When partial dates are present in the data, both a partial start date and/or a partial stop date will be evaluated to determine whether it can be conclusively established that the AE started prior to the start of study drug or ended prior to the start of study drug. If the above cannot be conclusively established based on the partial and/or present dates, then the AE will be considered as treatment-emergent.

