3.3 Subject Data and Study Conduct

3.3.1 *Subject Disposition*

The number and percentage of subjects in each of the following categories will be presented by the treatment group and overall for all screened subjects:

- screened,
- randomized,
- treated,
- randomized but not treated,
- completed the Treatment Period, and
- completed the study.

Primary reasons for discontinuation of study treatment and primary reasons for early withdrawal from the study will be tabulated.

3.3.2 *Protocol Deviations*

Any major protocol deviation will be documented as described in the protocol deviation plan, and its impact on inclusion in each analysis population for any subject will be specified. The final list of protocol deviations impacting the analysis populations will be reviewed prior to database lock. Counts and percentages of subjects with major protocol deviations by deviation category will be summarized for all randomized subjects.

3.3.3 *Analysis Populations*

Counts and percentages of subjects in each analysis population will be summarized by treatment and in total based on all randomized subjects.

3.3.4 *Demographic and Baseline Characteristics*

The following demographic and baseline characteristics will be summarized:

- Age (years)
- Sex
- Race
- Ethnicity
- COVID-19 severity (moderate or severe)
- NIAID Assessment
- $\text{PaO}_2:\text{FiO}_2$ ratio
- Pre-hospitalization oxygen requirement (None, Low-flow or High-flow Nasal cannula or CPAP mask)
- Concomitant medication to treat COVID-19 at baseline
- Comorbid conditions (diabetes, obesity, hypertension, heart failure, chronic kidney disease)

Demographic and baseline characteristics will be summarized with descriptive statistics or counts and percentages of subjects as appropriate by treatment group and overall for each Analysis Population.

3.3.5 *Medical History*

Medical history will be coded to system organ class and preferred term using the Medical Dictionary for Regulatory Activities (MedDRA) version 23.1. Counts and percentages of subjects with medical history by system organ class and preferred term will be summarized by treatment group and overall.

Counts and percentages of subjects with COVID-19 symptoms will be summarized by treatment group and overall.

3.3.6 *Concomitant Medications*

Concomitant medications will be coded to anatomical therapeutic chemical (ATC) class and preferred term using the World Health Organization Drug Dictionary (WHO Drug Global B3, March 2020).

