- All-cause mortality at Day 7 and Day 28; and
- Proportion of subjects who were discharged and remained free of respiratory failure prior to Day 7 and Day 28.

The following parameters will be analyzed using an analysis of variance (ANOVA) model with effects for treatment, baseline value and disease severity as factors:

- Change in $\text{PaO}_2:\text{FiO}_2$ ratio from baseline to Day 7 (or discharge) and baseline to Day 28 (or discharge),
- Length of hospitalization and not requiring invasive mechanical ventilation from baseline to Day 7 and baseline to Day 28 or death,
- Length of hospitalization from baseline to Day 7 and baseline to Day 28 or death,

Missing responses will be imputed using a multiple imputation (MI) method under the assumption of missing at random (MAR).

All results will be summarized descriptively by treatment group, along with corresponding 95% CI of the difference between razuprotafib groups vs. placebo, and p-value.

The length of hospitalization will include all days that the subject is admitted to the hospital. For subjects who are discharged and readmitted to the hospital, the length of hospitalization will include the days after readmission.

Hospitalization days will be counted in 24-hour periods; any partial days will be counted as a whole day.

Days that subjects are on the ventilator will be counted as days of respiratory failure. Days that subjects are of respiratory failure based on the definition will be counted as days of respiratory failure. For subjects receiving high flow oxygen by a nasal cannula or noninvasive positive

pressure ventilation when enrolled, the length of respiratory failure will include all the days of respiratory failure from baseline.

The time-to-event endpoint of time to reach grade 6, 7 or 8 on the NIAID 8-point ordinal scale will be summarized descriptively using the Kaplan-Meier method. The Kaplan-Meier estimate of the median time as well as the 2-sided 95% confidence interval will be presented by treatment group.

The endpoint of number of subjects in each category of the NIAID 8-point ordinal scale at Day 7 and Day 28 will be summarized by treatment group and timepoint using descriptive statistics.

The endpoint of time to return to prehospitalization oxygen requirement will be summarized by treatment group using descriptive statistics.

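### The SAP's single ANOVA includes a baseline value that the two hospital-length endpoints do not have, so their covariate either drops out or is left unspecified

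*SAP*

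**What the plan says.** SAP 3.4.1 places three parameters under one model, an "analysis of variance (ANOVA) model with effects for treatment, baseline value and disease severity as factors". The first is the change in PaO2:FiO2. The other two are "Length of hospitalization and not requiring invasive mechanical ventilation from baseline to Day 7 and baseline to Day 28 or death" and "Length of hospitalization from baseline to Day 7 and baseline to Day 28 or death". Each is to be reported with a 95% confidence interval against placebo and a p-value.

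SAP 3.1.2 fixes the meaning of baseline: "Baseline is defined as the last measurement prior to the first dose of study drug". The SAP names no other baseline covariate for the lengths.

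Protocol 9.2.1 has no baseline term: "Continuous efficacy endpoints will be analyzed using an analysis of variance model with effects for treatment and disease severity as factors". SAP Section 6 lists added and deleted endpoints and the percentage change for pharmacodynamic endpoints. It does not list the added baseline term.

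Clinical status is scheduled at Screening and, during treatment, "clinical status will be assessed TID, within 1 hour prior to each dose of study drug, using the NIAID 8-point ordinal scale" (Protocol Appendix A, footnote n). SAP 3.3.4 includes "NIAID Assessment" among the baseline characteristics to be summarized. No length model uses it. SAP 3.4.1 mentions other covariates only as an option, and does so under the Cochran-Mantel-Haenszel analyses.

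**The concern.** A length of stay that starts at baseline has no measurement before the first dose, so the model as written cannot be applied literally to two of the three endpoints it covers. There are two ways out, and the SAP does not choose between them. A programmer may treat the baseline of a length as the same constant for everyone, and the term vanishes. Or someone may decide that a different variable was meant, such as NIAID grade, PaO2:FiO2 or hospital days before dosing, possibly after data are available. Both endpoints carry p-values, so the covariate should not be open.

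There is also a modest missed opportunity. Severity has two levels, and the severe criteria in Protocol 4.1 are joined by or, with the note that "Patients receiving high flow oxygen by a nasal cannula or noninvasive positive pressure ventilation are permitted". One stratum can therefore hold subjects on high-flow or noninvasive support, on low-flow oxygen and on room air. The NIAID grade separates these, and it plausibly relates to length of stay.

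**Working it through.** The documents give no power, effect size or SD for these endpoints (SAP 2.2.4), so there is no planned figure to reproduce.

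**1. What the stated model fits.** Take Part 2 with 120 subjects in three arms (SAP 2.2.2). The design matrix has an intercept, two treatment indicators, severity and the baseline value: 5 columns. If the baseline value of a length is the same for every subject, its column is a multiple of the intercept. The computed rank is 4, whether the constant is 0 or 1, and the rank without the term is also 4. The fitted model is treatment plus severity, which is the model in Protocol 9.2.1.

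**2. Which grades can occur at entry.** Subjects are hospitalized (Protocol 4.1), which rules out grades 7 and 8. Invasive ventilation and ECMO are excluded (Protocol 4.2), which rules out grade 2. Grades 3 to 6 remain. Grouped as 3, 4, and 5 or 6, the grade uses two degrees of freedom, or one if a group is empty. Residual degrees of freedom in a three-arm Part 2 go from 120 − 4 = 116 to 114.

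**3. Precision from adding the grade.** Let R² be the share of variance left after treatment and severity that the grade explains. It is an assumption, because neither document gives a figure.

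- Confidence interval width is multiplied by √(1 − R²).
- Equivalent increase in subjects is 1/(1 − R²) − 1.
- Difference detectable with 80% power at two-sided 0.05, in units of the SD left after severity, is (1.960 + 0.842) × √[(1/n₀ + 1/n₁)(1 − R²)].

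For 40 against 40 with R² = 0: 2.802 × √(2/40) = 0.626 SD. For 40 against 80 (2:1 allocation, or pooled doses): 2.802 × √(1/40 + 1/80) = 0.543 SD.

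| Assumed R² | CI width × | Equivalent extra subjects | Detectable, 40 v 40 (SD) | Detectable, 40 v 80 (SD) |
|---|---|---|---|---|
| 0 | 1.000 | 0% | 0.626 | 0.543 |
| 0.05 | 0.975 | 5% | 0.611 | 0.529 |
| 0.10 | 0.949 | 11% | 0.594 | 0.515 |
| 0.20 | 0.894 | 25% | 0.560 | 0.485 |
| 0.30 | 0.837 | 43% | 0.524 | 0.454 |

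**4. Simulation check.** Lengths capped at 28 days were simulated for 120 subjects in three arms, half of them severe, with 1,500 runs per setting. The assumed grade mix (3/4/5) was 40/50/10% in severe and 0/40/60% in moderate subjects. The ratio of the standard error with the grade to that without was 1.01 when the grade carried no information, about 1.00 at a mean sample partial R² of 0.04, 0.96 at 0.11 and 0.91 at 0.20. These gains are slightly smaller than the formula gives (√(1 − 0.20) = 0.894, for example), because the formula ignores the degrees of freedom spent and the sample R² runs a little high. With no treatment effect, rejection rates were 3.7% to 6.2% across both models, with no clear departure from 5%.

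**The case against.** The strongest reply is that nothing breaks. If the baseline term drops out, what remains is the model the protocol specified, and it is valid. That stands. A reader might infer that the analysis of the two lengths cannot be run or would be biased; the documents do not support that.

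A second reply is that not using one of several candidate covariates is no error, since neither document promises adjustment for NIAID grade. That also stands. A reader might infer that the plan discards a large, known amount of information. No figure in the documents supports a size, and severity already uses SpO2 and PaO2:FiO2 criteria, so part of the oxygen-need contrast is in the model.

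Third, it goes too far to say as fact that every subject's baseline value is zero. Subjects are already in hospital at entry, and days before the first dose could be taken as a varying baseline. Counting from baseline makes this the less natural reading, but the text does not exclude it. This weakens the claim that the term must vanish and strengthens the point that the covariate is undefined.

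Fourth, calling the baseline value a factor could be read as one level per distinct PaO2:FiO2 value. That is mostly a matter of wording; an analyst would probably fit a continuous covariate. SAP Section 7 also defers programming detail to a separate document, which may settle some of this. A covariate for an inferential endpoint still belongs in the SAP.

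**Conclusion.** The point holds as a gap in specification with a small, optional gain in precision. For the two hospital-length endpoints the SAP's baseline term has no defined content: it either disappears, leaving the protocol's valid model, or it leaves the covariate open. The addition of the term to the protocol model is also unrecorded in SAP Section 6. This conclusion needs no assumption about R².

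The size of the gain does rest on one. It runs from nil, with a standard error about 1% wider if the grade is uninformative, to an interval about 5% narrower at R² = 0.10 and about 16% narrower at R² = 0.30. The upper end is illustrative. The respiratory-failure proportions at Day 7 and Day 28 use the Cochran-Mantel-Haenszel test and are unaffected. The change in PaO2:FiO2 needs only clearer wording. This is a worthwhile improvement, not a threat to the trial's conclusions.

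**What to change.** Before database lock, amend SAP 3.4.1 and Section 6 as follows.

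1. Analyse change in PaO2:FiO2 by analysis of covariance, with treatment and severity as factors and baseline PaO2:FiO2 as a continuous covariate.
2. Analyse the two length endpoints with treatment, severity and the last NIAID grade before the first dose as factors. Group the grade in advance as 3, 4, and 5 or 6. For subjects randomized but never dosed, who are in the ITT Population but have no pre-first-dose value by definition, use the Screening grade. Add one line on where a subject belongs who moves outside grades 3 to 6 between randomization and first dose.
3. List the departure from the protocol's treatment-plus-severity model in SAP Section 6.

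The cost is wording and one or two degrees of freedom. No new assessment is needed, because the grade is already scheduled at Screening and before each dose. A schedule does not guarantee completeness, so the SAP should also say that the Screening grade is used when the pre-dose grade is missing.

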7 EFFICACY, PHARMACODYNAMIC, AND PHARMACOKINETIC ASSESSMENTS

The efficacy endpoints include the following:

- Proportion of subjects alive and free of respiratory failure at Day 28;
- Proportion of subjects alive and free of respiratory failure at Day 7;
- Change in PaO₂:FiO₂ ratio from baseline to Day 7 (or discharge) and baseline to Day 28 (or discharge);
- Length hospitalized and free of respiratory failure from baseline to Day 7 and baseline to Day 28 or death;
- Length of hospitalization from baseline to Day 7 and baseline to Day 28 or death;
- Proportion of subjects who improve by ≥ 2 categories on the NIAID 8-point ordinal scale from baseline to Day 7 and baseline to Day 28;
- Proportion of subjects who worsen by ≥ 2 categories on the NIAID 8-point ordinal scale from baseline to Day 7 and baseline to Day 28;
- All-cause mortality at Day 7 and Day 28;
- Length of ICU stay from baseline to Day 28 or death;
- Number of subjects in each category of the NIAID 8-point ordinal scale at Day 7 and Day 28;
- Time to return to prehospitalization oxygen requirement; and
- Proportion of subjects who were discharged and remained free of respiratory failure prior to Day 7 and Day 28.

The pharmacodynamic and PK endpoints include the following:

- Change from baseline in CRP and D-dimer;
- Change from baseline in systemic biomarkers of vascular leakage and inflammation (ie, Angpt-2, IL-6, IL-8, TNF α , and HMGB-1);
- Summary of plasma concentrations of biomarkers at each sampling time point for each treatment group; and
- Summary of plasma razuprotafib concentrations for the samples collected on Day 1 and Day 6.

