6 CHANGES FROM PROTOCOL-SPECIFIED STATISTICAL ANALYSES

The protocol does not include the following three endpoints: proportion of subjects alive and not requiring invasive mechanical ventilation at any time through Day 28, time to reach grade 6, 7 or 8 on the NIAID 8-point ordinal scale, and length of hospitalization and not requiring invasive mechanical ventilation from baseline to Day 7 and baseline to Day 28 or death, these have been included in the SAP. The following two endpoints have been deleted from SAP: length of ICU stay from baseline to Day 28 or death has been deleted from SAP and length of hospitalized and free of respiratory failure from baseline to Day 7 and baseline to Day 28 or death.

The protocol does not include percentage change for PD endpoints, this has been included in the SAP.

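### SAP 3.4.1 tests hospital days without invasive ventilation by ANOVA, but the count has no direction of benefit and its value for deaths is ambiguous

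*SAP*

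**What the plan says.** SAP 3.4.1 lists three kinds of outcome for ANOVA: change in PaO₂:FiO₂ ratio, "Length of hospitalization and not requiring invasive mechanical ventilation from baseline to Day 7 and baseline to Day 28 or death", and "Length of hospitalization from baseline to Day 7 and baseline to Day 28 or death". The model has "effects for treatment, baseline value and disease severity as factors". On reporting it says: "All results will be summarized descriptively by treatment group, along with corresponding 95% CI of the difference between razuprotafib groups vs. placebo, and p-value".

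The composite is new in the SAP. The protocol (section 7) had "Length hospitalized and free of respiratory failure from baseline to Day 7 and baseline to Day 28 or death". SAP section 6 records that endpoint as deleted ("length of hospitalized and free of respiratory failure from baseline to Day 7 and baseline to Day 28 or death") and the IMV version as added, without a definition or a direction for the new one.

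Two counting rules follow the list in SAP 3.4.1. The first is "The length of hospitalization will include all days that the subject is admitted to the hospital", with readmission days included. The second is "Days that subjects are on the ventilator will be counted as days of respiratory failure", extended to any day meeting the respiratory-failure definition.

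SAP 3.1.6 has a general death rule. Where death is not a possible outcome of the endpoint, subjects who die before Day 28 receive the worst outcome at Day 28. No value in days is given.

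**The concern.** A day count that is tested needs a good end and a bad end. This one joins two quantities that pull in opposite directions. Time in hospital is better when short; time without IMV is better when long. Early discharge and prolonged intubation therefore both give low values.

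The surviving day-count text does not settle the matter. It defines respiratory-failure days, which under the SAP's definition include high-flow oxygen and noninvasive ventilation. Those days belonged to the deleted endpoint; they are not IMV days.

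The death value depends on which text governs. If the closing words about death end the count, an early death scores low. If the rule in SAP 3.1.6 applies, the worst outcome could be 0 days (no IMV-free time) or 28 days (longest stay), and choosing between them needs the missing direction. What is at stake is a reported difference, interval and p-value at two timepoints that nobody can call favourable or unfavourable.

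**Working it through.** The plan gives no event rates, standard deviation or effect size (SAP 2.2.4 states that no formal sizing was done), so there is no figure to reproduce. All rates below are assumptions.

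**1. Scoring single patients.** Composite = admitted days to Day 28 minus IMV days, with the count stopping at death.

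| Patient | Admitted | IMV | Composite | Days alive and IMV-free, death = 0 |
|---|---|---|---|---|
| Home on Day 4, never intubated | 4 | 0 | 4 | 28 |
| Intubated Days 5–28 | 28 | 24 | 4 | 4 |
| Dies on Day 4, never intubated | 4 | 0 | 4 | 0 |
| Intubated Days 5–14, on the ward Days 15–24 | 24 | 10 | 14 | 18 |
| Low-flow oxygen for 14 days, then home | 14 | 0 | 14 | 28 |

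The composite does not order these patients; the last column does.

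**2. Direction at arm level.** Assume 80% are discharged without IMV after a mean of 10 days, and 20% are intubated or die with a mean of 5 IMV-free hospital days.

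- Discharge one day earlier (benefit): 0.80 × (-1) = -0.80 days.
- Event group falls from 20% to 5% (benefit): 0.15 × (10 - 5) = +0.75 days.
- Event group rises from 20% to 35% (harm): 0.15 × (5 - 10) = -0.75 days.

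Two benefits have opposite signs, and one benefit looks like the harm. Ward days after extubation change the size. With 2.5 or 5 such days averaged over the event group, the harm becomes 0.15 × (7.5 - 10) = -0.38 or 0.15 × (10 - 10) = 0. For discharged means of 9 to 11 and event-group means of 4 to 6, it runs from 0.15 × (4 - 11) = -1.05 to 0.15 × (11 - 9) = +0.30. So preventing intubation can raise the mean but need not.

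A second set of assumptions, with 10% mortality in both arms, agrees.

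- Moving 15% of patients from long non-IMV stays (mean 20 days) to short ones (mean 7): 0.15 × (7 - 20) = -1.95 days.
- Moving 10% from intubated survivors (stay 21, IMV 11.5, so 9.5 IMV-free days) to long non-IMV stays: 0.10 × (20 - 9.5) = +1.05 days.

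Simulation with 40 per arm gave -1.91 to -1.98 and +1.03 to +1.08 across three death codings (count stops, 0, 28). Fixing the death value alone therefore does not create a direction. With identical arms, rejection stayed near 5% under every coding.

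**3. Death value in the composite.** With mortality p₁ and p₀, survivor mean m in both arms and death score x, the difference is (p₁ - p₀)(x - m). Take p₁ = 0.15, p₀ = 0.05 and m = 10, as higher-mortality arm minus lower.

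- Count stops at death on Day 8: 0.10 × (8 - 10) = -0.2 days.
- Death = 0: 0.10 × (0 - 10) = -1.0 days.
- Death = 28: 0.10 × (28 - 10) = +1.8 days.

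The two possible worst values lie 2.8 days apart, or 0.05 × 28 = 1.4 days at a 5-point mortality gap.

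**4. Plain length of hospitalization.** Stopping the count at death differs from scoring the full period by 0.10 × (28 - death day), under the same mortality. For mean death on Day 5, 8 or 12 this is 2.3, 2.0 or 1.6 days. At Day 7 it is small: with a mortality gap of 2 to 5 points and deaths on Days 5 to 3, 0.02 × (7 - 5) = 0.04 to 0.05 × (7 - 3) = 0.20 days.

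**The case against.** Four counter-arguments deserve weight.

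- **Death is not left open.** The endpoint's closing words most naturally stop the count at death, and the rule in SAP 3.1.6 is confined to endpoints in which death is not a possible outcome. This largely stands. A reader might infer that no death value can be determined at all, and the documents do not support that: there is a natural reading, with a rival one that the text does not exclude. SAP 3.4.1 also has a sentence giving the worst outcome to deaths before Day 7 or Day 28, but it sits with the CMH responder endpoints and does not settle the ANOVA endpoints.
- **The p-value is valid.** This stands. Once a coding is fixed, it tests equality of means at about the nominal level. A reader might infer inflated false-positive risk; the check shows none. Only interpretation is lost.
- **The name could mean length of stay among subjects never intubated, where shorter is better.** The SAP does not say so. It would select on a post-randomization event, against the SAP's statement that all efficacy analyses use the ITT Population.
- **Little hangs on it.** No efficacy endpoint is named primary, and all-cause mortality and survival without IMV through Day 28 have their own tests. This limits the severity but does not make the composite readable.

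**Conclusion.** The point holds in a limited form. Followed exactly, the SAP yields a difference, interval and p-value for the composite whose sign cannot be read as benefit or harm. That rests on the structure of the count and needs no assumed rate. The death value is ambiguous rather than absent. Under the assumed 15% against 5% mortality and 10-day survivor mean, the choice moves the result between -1.0 and +1.8 days, with -0.2 on the most natural reading.

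Plain length of hospitalization has an obvious direction, shorter being better, and shares only the death problem: an early death can count as a short stay. Under the same assumed mortality the two readings differ by 1.6 to 2.3 days at Day 28.

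A reader might conclude that the trial's efficacy findings as a whole are compromised. The documents do not support that, because the outcomes that matter most here are tested directly. It should be fixed, with moderate stakes.

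**What to change.** Amend SAP 2.3.1, 3.1.6 and 3.4.1, and list the changes in SAP section 6.

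- **Composite.** Replace it with days alive and free of IMV through Day 7 and through Day 28. State that more days is better, that any day with IMV counts as an IMV day, and that death by the timepoint scores 0.
- **Model.** Use ANOVA with treatment and disease severity, as in protocol 9.2.1. Omit the baseline-value term for day counts, where it has no stated meaning. A severity-stratified rank test with death ranked worst is an acceptable alternative if chosen before unblinding.
- **Minimum.** If the composite is kept, report it descriptively with no p-value.
- **Plain length of hospitalization.** Score death by the timepoint as the full 7 or 28 days, in line with the worst-outcome rule.

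The cost is SAP wording and derivations; no patients or visits are added. IMV days after discharge rest on readmission records, which the existing readmission rule already requires. There are three downsides. Resolution at Day 7 is limited. The new count gives no credit for earlier discharge, which length of hospitalization covers. Full-period scoring ties deaths with survivors still in hospital, so the mortality result should be read beside it.
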